8.1. Discontinuation from Study Treatment

8.1.1. Interruption of Investigational Product

In some circumstances, it may be necessary to temporarily interrupt treatment as a result of AEs or abnormal laboratory values that may have an unclear relationship to investigational product. It is recommended that the investigator consult with Lilly (or its designee) before temporarily interrupting therapy for reasons other than those defined in [Table JAIV.4](#). Unless otherwise specified, retest timing and frequency is at the investigator's discretion.

Investigational product that was temporarily interrupted because of an AE or abnormal laboratory value not specifically covered in [Table JAIV.4](#) may be restarted at the discretion of the investigator. Investigational product must be held in the following situations and may only be resumed as noted in the table.

Table JAIV.4. Criteria for Interruption of Investigational Product

Hold Investigational Product if the Following Abnormalities Occur:	Investigational Product May be Resumed When:
WBC count <2000 cells/ μ L (<2.00 x 10 ³ / μ L or <2.00 GI/L)	WBC count \geq 2500 cells/ μ L (\geq 2.50 x 10 ³ / μ L or \geq 2.50 GI/L)
ANC <1000 cells/ μ L (<1.00 x 10 ³ / μ L or <1.00 GI/L)	ANC \geq 1200 cells/ μ L (\geq 1.2 x 10 ³ / μ L or \geq 1.2 GI/L)
Lymphocyte count <500 cells/ μ L (<0.50 x 10 ³ / μ L or <0.50 GI/L)	Lymphocyte count \geq 750 cells/ μ L (\geq 0.75 x 10 ³ / μ L or \geq 0.75 GI/L)
Platelet count <75,000/ μ L (<75 x 10 ³ / μ L or <75 GI/L)	Platelet count \geq 100,000/ μ L (\geq 100 x 10 ³ / μ L or \geq 100 GI/L)
ALT or AST >3X ULN for patients with normal ALT or AST at baseline	ALT and AST return to \leq 3X ULN and investigational product is not considered the cause of enzyme elevation.
ALT or AST > 3X baseline value for patients with ALT or AST >ULN at baseline	ALT and AST return to \leq 3X baseline value for patients with increased baseline and investigational product is not considered the cause of enzyme elevation.
Hemoglobin <8 g/dL (<80.0 g/L)	Hemoglobin \geq 9 g/dL (\geq 90.0 g/L)
eGFR <50 mL/min/1.73 m ²	eGFR \geq 60 mL/min/1.73 m ²
Symptomatic herpes zoster	All skin lesions have crusted and are resolving
Infection that, in the opinion of the investigator, merits the IP being withheld ^a	Resolution of infection that, in the opinion of the investigator, merits the IP being restarted

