8.1.2. Permanent Discontinuation from Study Treatment

Possible reasons leading to permanent discontinuation of investigational product:

- **Subject Decision**
 - the patient requests to discontinue investigational product.
- **Investigator Decision**
 - the investigator decides that the patient should be discontinued from investigational product
- **Discontinuation due to a hepatic event or liver test abnormality:** Patients who are discontinued from investigational product because of a hepatic event or liver test abnormality should have additional hepatic safety data collected via eCRF. Details on continued hepatic monitoring are provided in Section 9.4.7.

If multiple values are obtained during screening, the highest value prior to receipt of investigational product will be used as baseline. Discontinuation of the investigational product for abnormal liver tests **should be** considered by the investigator when a patient meets one of the following conditions after consultation with the Lilly designated medical monitor:

- a. For patients with **baseline normal ALT and/or AST**, the following will result in discontinuation:

single laboratory test	ALT or AST >8 x ULN
single laboratory test	ALT or AST >3 x ULN and TBL >2 x ULN or International Normalized Ratio (INR) >1.5
single laboratory test	ALT or AST >3 x ULN with the appearance of fatigue, nausea, vomiting, right upper-quadrant pain or tenderness, fever, rash, and/or eosinophilia (>5%)
confirmed laboratory test (2 tests)	ALT or AST >2 x ULN and no other known cause.
during temporary interruption of IP	ALT or AST >5 x ULN for more than 2 weeks after temporary interruption of investigational product

- b. For patients with **baseline elevated ALT and/or AST**, the following will result in discontinuation:

confirmed laboratory test (2 tests)	ALT >5 x baseline, or >400 U/L (whichever occurs first)
confirmed laboratory test (2 tests)	ALT >3 x baseline and TBL >2 x ULN or INR >1.5
confirmed laboratory test (2 tests)	ALT >3 x baseline with appearance of severe fatigue, nausea, vomiting, right upper-quadrant abdominal pain, fever, rash, and/or eosinophilia (>5%)
confirmed laboratory test (2 tests)	ALT or AST >2 x ULN and no other known cause
confirmed laboratory test (2 tests)	TBL >1.5 x baseline upon retesting and no other known cause
during temporary interruption of IP	ALT >4 x baseline or >300 U/L (whichever occurs first) for more than 2 weeks after temporary interruption of investigational product

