9.4.7. Hepatic Safety Monitoring

If a study patient with ALT and AST within the normal range at baseline experiences elevated transaminases greater than 2x ULN, then a repeat measurement should be performed within 48 - 72 hours. If elevations greater than 2x ULN persist, then subjects should be evaluated for other causes of transaminase elevation and with additional tests of hepatic status. Close observation for suspected DILI will be conducted. If no other cause is found, then investigational product should be discontinued (see guidelines in Section 8.1).

If a study patient with ALT and AST above the normal range at baseline develops further elevations of ALT or AST >2x the baseline value or a bilirubin >2x ULN during the study, then repeat testing should be performed within 48 - 72 hours. If there are persistent elevations (ALT or AST >2x baseline or bilirubin >2x ULN), then close observation for suspected DILI will be conducted. If no other cause is found, then discontinuation of investigational product should be considered (see guidelines in Section 8.1).

The decision to discontinue or temporarily interrupt investigational product should be considered based on factors that include how much higher than baseline ALT and AST were relative to the upper limit of normal (ULN) and how much the on-study ALT and AST levels have increased relative to baseline, in addition to whether there is concomitant elevation of bilirubin or INR (see guidelines in Section 8.1).

If the patient lives in a remote area, repeat laboratory testing and close monitoring can be performed locally and the results should be promptly communicated to the investigator.

Close Observation for Suspected DILI

- Repeat liver enzyme and serum bilirubin tests two or three times weekly. Frequency of repeat testing can decrease to once a week or less if abnormalities stabilize or the trial drug has been discontinued and the subject is asymptomatic.
- Obtain a more detailed history of symptoms and prior or concurrent diseases.

- Obtain a history of concomitant drug use (including nonprescription medications and herbal and dietary supplement preparations), alcohol use, recreational drug use, and special diets.
- Rule out acute viral hepatitis types A, B, C, D, and E; autoimmune or alcoholic hepatitis; NASH; hypoxic/ischemic hepatopathy; and biliary tract disease.
- Obtain a history of exposure to environmental chemical agents.

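### For raised baseline ALT or AST, one stop row in Protocol 8.1.2 is tied to ULN while 9.4.7 rechecks against baseline, so a stable eligible value above 2 × ULN already meets the stop number

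*Protocol*

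**What the plan says.** Protocol 8.1.2 sets out three lists of liver-test conditions for permanent discontinuation. The lead-in says that stopping should be "considered by the investigator when a patient meets one of the following conditions after consultation with the Lilly designated medical monitor". List (a) covers "baseline normal ALT and/or AST", list (b) covers "baseline elevated ALT and/or AST", and list (c) covers all patients. The heading of each list is in mandatory terms. A later paragraph of the same section says that product should be stopped when a permanent threshold is met. That paragraph also allows repeat tests, and restart at the Table JAIV.4 levels, where another factor explains the value.

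Lists (a) and (b) share one row, to be confirmed by a second test: "ALT or AST >2 x ULN and no other known cause". List (b) has four other ALT rows, all expressed as multiples of the patient's own baseline. Two of them carry an absolute U/L alternative.

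Section 9.4.7 has two limbs. The first begins "If a study patient with ALT and AST within the normal range at baseline experiences elevated transaminases greater than 2x ULN" and leads to a repeat test, a search for other causes and, if none is found, discontinuation. The second is for patients with both enzymes above normal at baseline. It starts repeat testing at ALT or AST above twice the baseline value, or bilirubin above 2 × ULN, and if no other cause is found it says that discontinuation should be considered.

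Table JAIV.4 in 8.1.1 holds product at 3 × ULN "for patients with normal ALT or AST at baseline" and at 3 × baseline "for patients with ALT or AST >ULN at baseline". Exclusion criterion 29 removes ALT or AST above 3 × ULN. Criterion 44 removes a second screening value that is above ULN and more than 20% higher than the first.

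**The concern.** For normal baselines the two sections agree: list (a) and the first limb of 9.4.7 use the same number, a second test and the same cause condition. For raised baselines they do not. The permanent-stop row refers to ULN, and the recheck that would be expected to come before it refers to the patient's own baseline. A patient who entered with a stable ALT of 2.5 × ULN meets the number in the stop row on any two unchanged readings, yet 9.4.7 would not ask for a repeat test at that level.

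This is a safety stop rule. Two sites could read it differently for the same patient, each with support in the text. It also touches the primary analysis, because ALP observed after permanent discontinuation is left out of the MMRM (Protocol 10.3.1.2; SAP 6.3 and 6.3.2). That exclusion follows any permanent stop and is not peculiar to this row.

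**Working it through.** **Inputs.** Stop row: 2 × ULN, two tests (8.1.2, list (b)). Recheck: 2 × baseline (9.4.7, second limb). Temporary hold: 3 × baseline (8.1.1, Table JAIV.4). Eligibility: up to 3 × ULN if stable (criteria 29 and 44). The plan gives no figure of its own to reproduce here.

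**Formulas.** Let the enzyme's baseline be b × ULN with 1 < b ≤ 3, both enzymes above normal, and the same baseline value used in all three sections.
- Stop = 2 × ULN, which is 2/b × baseline.
- Recheck = 2b × ULN.
- Hold = 3b × ULN.
- Recheck minus stop = 2b − 2 = 2(b − 1) × ULN.

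| b | Stop (× ULN) | Recheck (× ULN) | Recheck − stop | Hold (× ULN) | Stop as multiple of baseline |
|---|---|---|---|---|---|
| 1.25 | 2.0 | 2.5 | 0.5 | 3.75 | 1.60 |
| 1.5 | 2.0 | 3.0 | 1.0 | 4.5 | 1.33 |
| 2.0 | 2.0 | 4.0 | 2.0 | 6.0 | 1.00 |
| 2.5 | 2.0 | 5.0 | 3.0 | 7.5 | 0.80 |
| 3.0 | 2.0 | 6.0 | 4.0 | 9.0 | 0.67 |

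The stop number is below the recheck number for every b above 1. For b above 2 the numeric part of the stop row is met with no rise at all. At b = 3, a 30% fall gives 3 × 0.70 = 2.1 × ULN, which still exceeds it.

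**Eligibility.** Two screening values of 2.5 × ULN have a ratio of 1.0, so criterion 44 is not met, and 2.5 is below the ceiling of 3 in criterion 29. Such a patient can enter.

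**Group definition.** Take a patient with ALT raised and AST normal at baseline.
- 8.1.2 joins the enzymes with *and/or*: the patient is in lists (a) and (b), 2 of 2.
- Table JAIV.4 uses *or*: the patient is in both hold rows, 2 of 2.
- 9.4.7 uses *and*: the patient is in neither limb, 0 of 2.

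**The case against.** The strongest defence has five parts.

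1. **Force.** A reader might infer that 8.1.2 commands a stop while 9.4.7 merely advises one. The documents do not support this as a conflict between the sections, because the lead-in to the lists in 8.1.2 also speaks of considering discontinuation, after consultation. The tension lies inside 8.1.2, between its lead-in, its list headings and its later paragraph, and it affects all three lists. It still needs resolving.

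2. **Which section governs.** Section 9.4.7 points to Section 8.1 each of the three times it discusses stopping, whereas 8.1.2 points the other way only for monitoring: "Details on continued hepatic monitoring are provided in Section 9.4.7". The natural reading is that 8.1 governs stopping. That is fair, but it leads back to the ULN-based row and leaves a recheck set above the stop.

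3. **Cause condition.** A reader might infer a dilemma: either PBC counts as another cause and the row is void for everyone enrolled, or it does not and the row catches every stable patient above 2 × ULN. The documents do not force that choice. An elevation present before the first dose cannot be due to study drug, and treating it as a known other cause spares the stable patient while keeping the row for new rises. This reading is sensible, but the protocol does not state it.

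4. **Softening text.** The row needs two tests. Section 9.4.7 directs attention to the change from baseline, which is nil in a stable patient. The medical monitor is consulted, and 8.1.2 allows repeat tests and restart. Scheduled chemistry continues at Weeks 1, 4, 8 and 12. All of this lowers the chance of a needless stop. None of it names the reference value.

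5. **Group wording.** The 8.1.2 wording can be read enzyme by enzyme, and the row then has a coherent use for an enzyme that was normal at baseline. The text does not limit it to that use. A patient with one enzyme raised is still covered by the general decision paragraph of 9.4.7.

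**Conclusion.** The point stands as a contradiction in reference value, with a secondary gap in group definition. For raised baselines the recheck number exceeds the stop number by 2(b − 1) × ULN, from 0.5 × ULN at b = 1.25 to 4.0 × ULN at b = 3. For eligible baselines above 2 × ULN, the number in the stop row is met without any change. Whether the row then applies depends on a cause condition that the protocol leaves undefined for elevations present before dosing.

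This assumes both enzymes are raised, one common baseline value across the sections, and b no higher than the eligibility ceiling.

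A reader might go further and infer that such patients must be stopped, that the stop lying below the temporary hold is itself the error, or that the primary comparison loses power. The documents support none of these. The cause condition and the consultation stand between the number and a stop. List (a) also has a stop (2 × ULN, confirmed) below its hold (3 × ULN). The number of patients affected cannot be derived, so no power loss can be claimed.

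**What to change.** The sponsor should reconcile 8.1.1 (Table JAIV.4), 8.1.2 (lead-in, list headings, lists (a) and (b), and the later paragraph on repeat tests and restart) and 9.4.7, checked against criteria 29 and 44, on four points:
- the reference value, ULN or own baseline, for the raised-baseline group;
- the definition of that group, including patients with only one enzyme raised;
- whether a known elevation before dosing counts as another known cause;
- whether meeting a listed condition makes stopping mandatory or a matter for consideration.

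No threshold or clinical rule is proposed here; that choice belongs to the sponsor. The cost is amendment wording in three sections and possibly a small change in the number of repeat liver tests, depending on how the sponsor settles it.

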8.1.3. Discontinuation of Inadvertently Enrolled Patients

If the sponsor or investigator identify a patient who did not meet enrollment criteria and was inadvertently enrolled, then the patient should be discontinued from study treatment unless there are extenuating circumstances that make it medically necessary for the patient to continue on study treatment. If the investigator and the sponsor designated medical monitor agree it is medically appropriate to continue, the investigator must obtain documented approval from the sponsor designated medical monitor to allow the inadvertently enrolled patient to continue in the study with or without treatment with investigational product. Safety follow-up is as outlined in Section 2 (Schedule of Activities), Section 9.2 (Adverse Events), and Section 9.4 (Safety) of the protocol.

8.2. Discontinuation from the Study

Patients will be discontinued in the following circumstances:

- enrollment in any other clinical study involving an investigational product or enrollment in any other type of medical research judged not to be scientifically or medically compatible with this study
- participation in the study needs to be stopped for medical, safety, regulatory, or other reasons consistent with applicable laws, regulations, and good clinical practice (GCP)
- investigator decision
 - the investigator decides that the patient should be discontinued from the study
 - if the patient, for any reason, requires treatment with another therapeutic agent that has been demonstrated to be effective for treatment of the study indication, discontinuation from the study occurs prior to introduction of the new agent
- subject decision
 - the patient requests to be withdrawn from the study

Patients discontinuing from the study prematurely for any reason should complete AE and other safety follow-up per Section 2 (Schedule of Activities), Section 9.2 (Adverse Events), and Section 9.4 (Safety) of this protocol.

8.3. Lost to Follow-up

A patient will be considered lost to follow-up if he or she repeatedly fails to return for scheduled visits and is unable to be contacted by the study site. Site personnel are expected to make diligent attempts to contact patients who fail to return for a scheduled visit or were otherwise unable to be followed up by the site.

9. Study Assessments and Procedures

Section 2 lists the Schedule of Activities, with the study procedures and their timing (including tolerance limits for timing).

Appendix 2 lists the laboratory tests that will be performed for this study.

Unless otherwise stated in the subsections below, all samples collected for specified laboratory tests will be destroyed within 60 days of receipt of confirmed test results. Certain samples may be retained for a longer period, if necessary, to comply with applicable laws, regulations, or laboratory certification standards.

9.1. Efficacy Assessments

9.1.1. Primary Efficacy Assessments

The primary efficacy assessment in Study JAIV will be change in ALP at Week 12.

9.1.2. Secondary and Exploratory Efficacy Assessments

Secondary efficacy assessments will include the proportion of patients with ALP $<1.67 \times$ ULN (and at least 15% decrease from baseline), Itch NRS, fatigue NRS. Exploratory efficacy assessments will include Functional Assessment of Chronic Illness Therapy-Fatigue (FACIT-F), PBC-40, and total bilirubin.

The Itch NRS is a patient-administered, 11-point horizontal scale anchored at 0 and 10, with 0 representing “no itch” and 10 representing “worst itch imaginable.” Overall severity of a patient’s itching is indicated by selecting the number that describes the worst level of itching in the past 7 days.

The Fatigue NRS is a single-item, patient-administered, 11-point horizontal scale anchored at 0 and 10, with 0 representing “no fatigue” and 10 representing “as bad as you can imagine.” Overall severity of a patient’s fatigue is indicated by selecting the number that describes the worst level of fatigue during the past 7 days.

The FACIT-F measures an individual’s self-reported level of fatigue during their usual daily activities over the past 7 days. The scale is composed of 13 items measured on a 4-point Likert scale (4 = very much to 0 = not at all). The total score ranges from 0 to 52, and higher scores representing less fatigue. A score of less than 30 indicates severe fatigue (Webster et al. 2003).

The PBC-40 is a disease-specific, 40-item, patient-reported survey containing 6 domains: overall symptoms, itch, fatigue, cognition, social, and emotional. Response options for overall symptoms, itch, fatigue, and cognition are on a 5-point scale: “Never,” “Rarely,” “Sometimes,” “Most of the time,” and “Always.” Response options are also on a 5-point scale for social and emotional: “Not at all,” “A little,” “Somewhat,” “Quite a bit,” and “Very much.” Items are scored from 1 to 5 and the individual item scores are summed to give a total domain score where high scores represent high impact of PBC on quality of life (Jacoby et al. 2005).

The Physician's Global Assessment of Disease Activity is the physician's assessment of the patient's overall disease activity due to PBC, as compared with all possible patients with PBC. The Physician's Global Assessment of Disease Activity is scored using a 100-mm visual analog scale (VAS), where 0 mm (measured from the left starting point of the line) indicates no disease activity and 100 mm (measured from the left starting point of the line) indicates the most severe disease activity possible for all patients with PBC. The Physician's Global Assessment of Disease Activity score is indicated by making a vertical tick mark on the line between 0 and 100 mm. There are benchmarks of 0 (0 mm), 1 (33 mm), 2 (67 mm), and 3 (100 mm) on the line corresponding to no, mild, moderate, and severe PBC disease activity, respectively.

9.1.3. Appropriateness of Assessments

Itch and fatigue are 2 prevalent and bothersome symptoms to PBC patients. The PBC-40 is a disease-specific quality of life measure developed for PBC.

9.2. Adverse Events

Investigators are responsible for monitoring the safety of patients who have entered this study and for alerting Lilly or its designee to any event that seems unusual, even if this event may be considered an unanticipated benefit to the patient.

The investigator is responsible for the appropriate medical care of patients during the study.

Investigators must document their review of each laboratory safety report.

The investigator remains responsible for following, through an appropriate health care option, AEs that are serious or otherwise medically important, considered related to the investigational product or the study, or that caused the patient to discontinue the investigational product before completing the study. The patient should be followed until the event resolves, stabilizes with appropriate diagnostic evaluation, or is reasonably explained. The frequency of follow-up evaluations of the AE is left to the discretion of the investigator.

Lack of drug effect is not an AE in clinical studies, because the purpose of the clinical study is to establish treatment effect.

After the ICF is signed, study site personnel will record via eCRF the occurrence and nature of each patient's preexisting conditions, including clinically significant signs and symptoms of the disease under treatment in the study. In addition, site personnel will record any change in the condition(s) and any new conditions as AEs. Investigators should record the following via the eCRF for each AE: time of onset, time of termination, severity and their assessment of the potential relatedness of each AE to protocol procedure or investigational product.

The investigator will interpret and document whether or not an AE has a reasonable possibility of being related to study treatment, or a study procedure, taking into account the disease, concomitant treatment or pathologies.

A "reasonable possibility" means that there is a cause and effect relationship between the investigational product and/or study procedure and the AE.

The investigator answers yes/no when making this assessment.

Planned surgeries and nonsurgical interventions should not be reported as AEs unless the underlying medical condition has worsened during the course of the study.

If a patient's investigational product is discontinued as a result of an AE, study site personnel must report this to Lilly or its designee via eCRF, clarifying if possible, the circumstances leading to any dosage modifications, or discontinuations of treatment.

